6.6.3 Exploratory Endpoints Analysis

[REDACTED]

[REDACTED]

[REDACTED]

[REDACTED]

[REDACTED]

[REDACTED]

[REDACTED]

6.6.4 Subgroup Analyses

Please see Section 6.6.1.3.

CONFIDENTIAL

6.7 Safety Analysis

Safety will be evaluated by the frequency of AEs, severity and type of AEs, and by changes from baseline in patients' vital signs, weights, ECOG performance status, ECG results, and clinical laboratory results.

All safety analyses will be performed using the safety population. Unless otherwise specified, all safety analyses will be reported according to actual study treatment received.

6.7.1 Adverse Events

Adverse events will be coded using the Medical Dictionary for Regulatory Activities (MedDRA) Version 25.0 or later (based on the version at time of database lock) with the severity graded by the NCI CTCAE Version 5.0 or later (based on the version at time of database lock). Treatment-emergent is defined as any AE that occurs after administration of the first dose of any study drug through 30 days after the last dose of any study drug.

Treatment-emergent AEs will be summarized by MedDRA system organ class (SOC) and preferred term (PT) by dose level. For summary tabulations the following hematologic abnormalities coded to MedDRA preferred terms in the Investigations SOC will be pooled with the appropriate clinical terms in the Blood and lymphatic system disorders SOC:

MedDRA Preferred Term (Investigation SOC)	Mapped to (Blood and lymphatic system disorders SOC)
Neutrophil count decreased	Neutropenia
Platelet count decreased	Thrombocytopenia
Hemoglobin decreased	Anemia
White blood cell count decreased	Leukopenia
Lymphocyte count decreased	Lymphopenia

Summary tabulations will include the following categories by SOC/PT unless otherwise specified:

- Treatment-emergent AEs (by PT as well).
- Drug-related treatment-emergent AEs.

- Grade 3 or higher treatment-emergent AEs.
- Grade 3 or higher drug-related treatment-emergent AEs.
- Grade 3 and Grade 4 treatment-emergent AEs (based on maximum severity, by PT as well).
- Grade 5 treatment-emergent AEs.
- Grade 5 drug-related treatment-emergent AEs.
- The most commonly reported treatment-emergent AEs (i.e., those events reported by $\geq 10\%$ of all patients, by PT only).
- Serious treatment-emergent adverse events (SAEs) (based on maximum severity).
- Drug-related treatment-emergent SAEs.
- Grade 3 or higher treatment-emergent SAEs.
- Grade 3 or higher drug-related treatment-emergent SAEs.
- Grade 3 and Grade 4 treatment-emergent SAEs (based on maximum severity).
- Grade 3 and Grade 4 drug-related treatment-emergent SAEs (based on maximum severity).
- Treatment-emergent AEs resulting in discontinuation of study drug.
- Treatment-emergent AEs resulting in study drug modifications (including discontinuation, delay, reduction, and interruption).
- Treatment-emergent AEs resulting in dose delays.
- Treatment-emergent AEs resulting in dose reductions.
- Treatment-emergent AEs resulting in infusion rate reductions
- Treatment-emergent AEs resulting in drug interruptions.
- Treatment-emergent AEs resulting in drug infusion interruptions.
- Treatment-emergent AESIs – all Grades (by PT as well).
- Treatment-emergent AESIs Grade 3 or Grade 4.
- Treatment-emergent AESIs Grade 5.
- Serious treatment-emergent AESIs.

All summaries will be by dose levels by phases (phase 1 escalation and phase 2a dose finding) for patients in the safety population.

Patients with the same AE more than once will have that event counted only once within each SOC, and once within each preferred term. Patients with the same AE more than once will have only the maximum intensity of that event counted once within each SOC, and once within each preferred term.

Most commonly reported (at least 10% of all patients) treatment-emergent AEs will be presented by preferred term only. Patients with multiple occurrences of the same AE will have that event counted only once within each preferred term.

An overall summary treatment-emergent AE table will include numbers and percentages of patients who had any treatment-emergent AE, drug-related treatment-emergent AE, Grade 3 or higher treatment-emergent AE, grade 3 or higher drug-related treatment-emergent AE, serious treatment-emergent AE, drug-related serious treatment-emergent AE, serious treatment-emergent AE leading to study drug discontinuation, treatment-emergent AE resulting in study drug discontinuation, and on-study deaths. On-study death is defined as deaths that occur between the first dose of study drug and up to 30 days after the last dose of study drug and deaths that occur more than 30 days after the last dose of study drug but are assessed as study drug-related.

A by-patient listing of DLTs as identified by the investigator that occur during Cycle 1 of treatment will be presented by dose levels for all patients enrolled during the phase 1 dose escalation portion of this study. Patients will be grouped by the dose level to which they were originally assigned, including those who receive subsequent treatment at a lower or higher dose level.

A by-patient listing of all deaths regardless of whether on study or not will also be presented. In this listing, on-study deaths will be flagged.

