**Table 6.a Primary and Secondary Endpoints for Disclosures**

Endpoint	Definition	Maximum Time Frame
Phase 1 Dose Escalation		
Primary: DLT incidences	Section 8.3.1	Up to 60 months
Primary: Frequency and severity of TEAEs	Section 13.1.8	Up to 60 months
Secondary: Summary PK statistics for modakafusp alfa in Cycles 1 and 2	Sections 5.2.2 and 13.1.4	Up to 60 months
Secondary: Summary PK statistics for daratumumab in Cycles 1 and 2	Sections 5.2.2 and 13.1.4	Up to 60 months
Secondary: ORR by investigator	Section 13.1.3.1	Up to 60 months
Secondary: DOR by investigator	Section 13.1.3.2.1	Up to 60 months
Secondary: PFS by investigator	Section 13.1.3.2.1	Up to 60 months
Secondary: OS	Section 13.1.3.2.1	Up to 60 months
Secondary: ADA incidence and characteristics and NAb	Section 13.1.7	Up to 60 months
Secondary: Rate of MRD[-] CR by investigator	Section 13.1.3.2.1	Up to 60 months
Secondary: Rate of MRD[-]	Section 13.1.3.2.1	Up to 60 months
Secondary: Duration of MRD negativity	Section 13.1.3.2.1	Up to 60 months
Phase 2a Dose Finding		
Primary: ORR	Section 13.1.3.1	Up to 60 months
Secondary: DOR by investigator	Section 13.1.3.2.2	Up to 60 months
Secondary: CBR by investigator	Section 13.1.3.2.2	Up to 60 months
Secondary: DCB by investigator	Section 13.1.3.2.2	Up to 60 months
Secondary: DCR (CBR + SD) by investigator	Section 13.1.3.2.2	Up to 60 months
Secondary: Duration of disease control by investigator	Section 13.1.3.2.2	Up to 60 months
Secondary: TTP by investigator	Section 13.1.3.2.2	Up to 60 months
Secondary: TTR by investigator	Section 13.1.3.2.2	Up to 60 months
Secondary: TTNT	Section 13.1.3.2.2	Up to 60 months
Secondary: PFS by investigator	Section 13.1.3.2.2	Up to 60 months
Secondary: OS	Section 13.1.3.2.2	Up to 60 months
Secondary: Frequency and severity of TEAEs	Section 13.1.8	Up to 60 months
Secondary: ADA incidence and characteristics and NAb	Section 13.1.7	Up to 60 months
Secondary: Rate of MRD[-] CR by investigator	Section 13.1.3.2.2	Up to 60 months
Secondary: Rate of MRD[-]	Section 13.1.3.2.2	Up to 60 months
Secondary: Duration of MRD negativity	Section 13.1.3.2.2	Up to 60 months

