#### **9.5.7      Concomitant Medications and Procedures**

Any prior or concomitant medication a patient has had from signing of the ICF through 30 (+10) days after the last dose of study drug treatment (modakafusp alfa and/or daratumumab SC) or the start of subsequent systemic anticancer therapy, whichever occurs first, will be recorded on the eCRF. Trade name and international nonproprietary name (if available), indication, and start and end dates of the administered medication will be recorded. Medications used by the patient and therapeutic procedures (including any transfusion) completed by the patient will be recorded in the eCRF. See Sections 8.7 and 8.8 regarding medications and therapies that are prohibited or allowed, respectively, during the study.

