**Relationship** of the event to study drug administration (ie, its causality) will be determined by the investigator responding yes (related) or no (unrelated) to this question: Is there a reasonable possibility that the AE is associated with the study drug?

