### 10.3 Monitoring of AEs and Period of Observation

AEs, both nonserious and serious, will be monitored throughout the study as follows:

- AEs will be reported from the signing of informed (e)consent through 30 days after administration of the last dose of study drug or start of subsequent anticancer therapy, whichever occurs first and recorded in the eCRFs.
- SAEs will be reported to the Takeda Global Pharmacovigilance department or designee from the signing of informed (e)consent through 30 days after administration of the last dose of study drug, even if the patient starts nonprotocol therapy and recorded in the eCRF. After this period, only related SAEs must be reported to the Takeda Global Pharmacovigilance department or designee. SAEs should be monitored until they are resolved or are clearly determined to be due to a patient's stable or chronic condition or intercurrent illness(es).

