## 13.0 STATISTICAL METHODS

### 13.1 Statistical and Analytical Plans

In general, summary tabulations will be presented by dose level for the phase 1 dose escalation and phase 2a dose finding, and will display the number of observations, mean, standard deviation, median, minimum, and maximum for continuous data, and the number and percentage per category for categorical data. The Kaplan-Meier (K-M) survival curves and 25th, 50th (median), and 75th percentiles (if estimable) will be provided along with their 95% CIs for time-to-event data.

Deviations from the statistical analyses outlined in this protocol will be indicated in the statistical analysis plan; any further modifications will be noted in the final clinical study report.

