### **13.1.8 Safety Analysis**

AEs will be summarized using the safety population.

Safety will be evaluated by the frequency of AEs, severity, and types of AEs, and by changes from baseline in patients' vital signs, weights, ECOG performance status, ECG results, and clinical laboratory results using the safety analysis set.

Exposure to study drug over time will be summarized with time on treatment, total amount of administered treatment, dose intensity, and relative dose intensity. Reasons for treatment discontinuation and modification will be tabulated.

TEAEs that occur after administration of the first dose of study drug and through 30 days after the last dose of study drug or start of subsequent anticancer therapy, whichever occurs first will be tabulated. All AEs will be coded using the Medical Dictionary for Regulatory Activities. Data will be summarized using Preferred Term and/or primary System Organ Class and will include the following categories:

- TEAEs.
- Drug-related TEAEs.
- Grade 3 or higher TEAEs.
- Grade 3 or higher drug-related TEAEs.
- Grade 5 TEAEs.
- Grade 5 drug-related TEAEs.
- The most commonly reported TEAEs (ie, those reported by  $\geq 10\%$  of all patients).
- SAEs (related and regardless of relationship).
- SAEs Grade 3 or higher.
- Drug-related SAEs Grade 3 or higher.
- AESIs Grade 3 or higher.
- TEAE leading to study drug modification and discontinuation.

The incidence of DLTs will be tabulated using the DLT-evaluable population.

Descriptive statistics for the actual values of clinical laboratory parameters (and/or change from baseline in clinical laboratory parameters) will be presented for all scheduled measurements over time. Mean laboratory values over time will be plotted for key laboratory parameters.

Shift tables for laboratory parameters will be generated for changes in NCI CTCAE grade from baseline to the worst postbaseline value. Graphical displays of key safety parameters, such as scatter plots of baseline versus worst postbaseline values, may be used to understand the modakafusp alfa safety profile.

Descriptive statistics for the actual values (and/or the changes from baseline) of vital signs, weight and ECOG performance status scores will be tabulated by scheduled time points.

Physical examination findings will be presented in the data listings.

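### SAP 6.7.1 drops the protocol's TEAE cut-off at the start of subsequent anticancer therapy, adding a stretch of follow-up in which only serious events are required

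*SAP*

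**What the plan says.** The two documents end the TEAE window differently.

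- **SAP 6.7.1:** from the first dose of any study drug "through 30 days after the last dose of any study drug". Subsequent therapy is not mentioned.
- **Protocol 13.1.8:** TEAEs "through 30 days after the last dose of study drug or start of subsequent anticancer therapy, whichever occurs first will be tabulated".

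Table 6.a of the protocol, in the row "Primary: Frequency and severity of TEAEs" for Phase 1, gives Section 13.1.8 as the definition. The Phase 2a secondary TEAE endpoint points to the same section.

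Data collection is set in protocol 10.3. AEs are reported "through 30 days after administration of the last dose of study drug or start of subsequent anticancer therapy, whichever occurs first". SAEs are reported "through 30 days after administration of the last dose of study drug, even if the patient starts nonprotocol therapy". The Schedules of Events repeat both rules. Under protocol 9.5.7, concomitant medication is recorded through 30 (+10) days after the last dose or "the start of subsequent systemic anticancer therapy, whichever occurs first, will be recorded on the eCRF".

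On differences between the documents, protocol 13.1 states: "Deviations from the statistical analyses outlined in this protocol will be indicated in the statistical analysis plan".

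**The concern.** The protocol's TEAE window matches its AE collection window; the SAP's does not. After an early switch, the SAP keeps counting events while the patient is on another treatment, and the only events required to be reported in that period are serious ones. Relative to the protocol definition, the change can only add events, and those added will be mainly serious.

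TEAE frequency and severity is a primary endpoint in Phase 1 and a secondary endpoint in Phase 2a, and SAP 6.7.1 tabulates it by dose level. Serious, Grade 3 or higher and Grade 5 rates by dose could then partly reflect the next therapy. Concomitant medication recording also stops at the switch, which makes those events harder to interpret.

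The SAP does use the start of subsequent therapy elsewhere: for confirming response, for best overall response (6.6.1.2) and for PFS censoring (Table 1). It gives no reason for treating safety differently, so this looks like an omission rather than a policy.

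**Working it through.** **Step 1: set the windows side by side.** Let d be the day after the last dose on which subsequent therapy starts, with d between 0 and 30.

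| Period after last dose | Non-serious AEs required (10.3) | SAEs required (10.3) | In protocol TEAE window (13.1.8) | In SAP TEAE window (6.7.1) |
|---|---|---|---|---|
| Day 0 to d | Yes | Yes | Yes | Yes |
| Day d to 30 | No | Yes | No | Yes |

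Only the second row differs. The protocol window ends at min(30, d) and the SAP window at 30, so the added stretch is 30 - min(30, d) days.

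**Step 2: length of the added stretch.** The documents give no switch times, so d runs over its range.

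| d | 30 - d (days with SAEs only) |
|---|---|
| 0 | 30 |
| 7 | 23 |
| 14 | 16 |
| 21 | 9 |
| 28 | 2 |
| 30 or later | 0 |

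**Step 3: effect on a rate.** If k of n patients have a serious TEAE under the protocol window, and one further patient has a first serious TEAE in the added stretch, the rate goes from k/n to (k + 1)/n, a shift of 1/n.

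- n = 6 (the most a rolling six dose level takes under protocol 8.4): 1/6 = 16.7 points.
- n = 18 (approximate Phase 1 target): 1/18 = 5.6 points.
- n = 20 (approximate Phase 2a arm): 1/20 = 5.0 points.

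If that patient already had a serious TEAE, the overall rate moves by 0 points; only a system organ class or preferred term row can change.

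**Step 4: which tables can move.** The all-causality tables are exposed: all TEAEs, Grade 3 or higher, Grade 5, serious, and most common. Drug-related tables are partly protected because the investigator answers the causality question in protocol 10.2, "Is there a reasonable possibility that the AE is associated with the study drug". Cycle 1 DLTs and escalation decisions are not the issue. Tables of dose delay, reduction, interruption or infusion-rate change are essentially untouched by events after the last dose, and so are the AESI tables, because the AESIs are infusion-related reactions.

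**Step 5: is the change declared?** The SAP text available, redactions aside, contains no section on changes from the protocol and no note on this window. There is no figure in the plan to reproduce on this point.

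**The case against.** The strongest reply is that the SAP window is the inclusive choice for safety and follows a window the protocol itself uses: SAEs are collected to day 30 whatever the patient starts next, and SAP 6.7.1 uses the same 30 days for on-study deaths. Cutting at the switch moves a few SAEs, possibly including late study-drug effects, from tables to a listing. That is a real cost in a programme that amended its protocol because of fatal bleeding risk. The protocol also permits deviations that the SAP indicates, so declaring the longer window and showing post-switch SAEs separately would remove the inconsistency too. That much stands. But the longer window is inclusive only for serious events, and as far as can be seen the deviation is not declared.

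The size is also open to challenge. No count of early switchers exists. Daratumumab is given weekly in Cycles 1 and 2, every 2 weeks in Cycles 3 to 6, and every 4 weeks after that. A patient who stops undosed at a scheduled Day 1 is therefore nominally 7 days from the last dose at Cycles 2 and 3, 14 days at Cycles 4 to 7, and 28 days from Cycle 8. For such a patient the added stretch is at most 23, 16 or 2 days, although someone dosed before results return, or stopping mid-cycle, could switch sooner. The 18 is a DLT-evaluable target, while TEAE tables use everyone dosed, so the Phase 1 shift may be below 5.6 points. Appendix G records a sponsor decision not to proceed to Phase 2a, so the 5.0-point example may have no practical bearing.

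Finally, the amount of non-serious AE data required is the same under either definition, because protocol 10.3 fixes it. No data are lost; the SAP adds a period observed for SAEs only. These points limit the effect but do not remove the conflict.

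**Conclusion.** The point holds. SAP 6.7.1 widens the window of a Phase 1 primary endpoint beyond its protocol definition, and the added part has asymmetric reporting. The text difference and the asymmetry are certain. The absence of a declared deviation is as far as the available SAP text shows.

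The effect is confined to patients who start another anticancer therapy within 30 days of the last dose, and mainly to all-causality tables. The shifts of 16.7, 5.6 and 5.0 points are per affected patient and assume that the patient's only serious TEAE falls after the switch. They are not estimates of what will happen. This should be corrected before the safety tables are produced; it does not put the dose-escalation decisions in doubt.

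**What to change.** In SAP 6.7.1, end the TEAE window at the earlier of 30 days after the last dose of any study drug and the start of subsequent anticancer therapy, as protocol 13.1.8 does. The added stretch then falls from 30 - d days to 0.

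Alongside this:

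- List SAEs that begin after the switch and up to day 30 separately, by dose level, so that possible late study-drug effects stay visible. Identify post-switch deaths in the listing of all deaths that the SAP already plans.
- State how on-study deaths relate to Grade 5 TEAEs. With the cut-off restored, a death by day 30 from an event that began after the switch would be an on-study death but not a Grade 5 TEAE.

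If the sponsor prefers the 30-day window, the SAP should declare and justify the deviation and show post-switch SAEs separately.

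The cost is a change of wording and one date condition in the adverse event dataset, using the subsequent-therapy date already needed for PFS censoring and TTNT. The downside is that a few SAEs move from the tables to a listing.

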6.7.2 Adverse Events of Special Interest

AE of special interest from a scientific and medical perspective (AESI) will be reported by SOC and preferred terms. In this study, infusion-related reactions (IRR) are considered as AESIs. The IRR signs and symptoms will be counted with other AEs in the treatment-emergent AE tables with other AEs, and also reported separately in AESI tables.

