#### 4.3 Modakafusp Alfa Starting Dose Justification for the Phase 1 Dose Escalation in Combination With Daratumumab SC

The initial dose level to be evaluated for modakafusp alfa in the phase 1 dose escalation in combination with daratumumab SC will be 80 mg Q4W, which is N-1 or N-2 of the potential modakafusp alfa single agent doses of 120 mg or 240 mg Q4W, respectively, which are currently being assessed in Part 3 of Study TAK-573-1501 for selection of an optimal single agent dose. The dosing of daratumumab SC will be 1800 mg every week (QW) for Cycles 1 and 2, once

every 2 weeks (Q2W) for Cycles 3 to 6, and Q4W thereafter in 28-day cycles (see Section 8.1.2 for additional dosing information).

At the modakafusp alfa 80 mg Q4W dose, the median single-dose AUC is expected to be approximately 3- and 6-fold below the potential single agent dose of 120 mg or 240 mg Q4W, respectively.

On the basis of the single-agent safety profile of modakafusp alfa from Study TAK-573-1501 described in Section 4.1.2.2, the major potential overlapping toxicities anticipated with modakafusp alfa in combination with daratumumab SC are thrombocytopenia and neutropenia, with the possible clinical manifestation of bleeding and infection. As such, these clinical events were analyzed in patients treated with modakafusp alfa (Study TAK-573-1501) at the body weight-based Q3W and Q4W dosing schedule equivalent to flat dose of 70 to 90 mg. Only 1 of 10 patients in this group reported a treatment-emergent adverse event (TEAE) within the System Organ Class of infections and infestations, which was an event of oral herpes. This event was assessed as Grade 2 and unrelated to modakafusp alfa. There was 1 TEAE of Grade 1 epistaxis which was assessed as unrelated to modakafusp alfa.

In addition, in the same 10 patients treated with equivalent flat dose of 70 to 90 mg, ORR responses were observed in 3 of 10 patients (30%). Clinical efficacy at doses <70 mg was very limited, with 1 of 19 patients (5%) with a reported response.

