### **8.6.1.3 Criteria for Dose Interruption**

All toxicities that occur during the study will be actively managed following the standard of care unless otherwise specified in the protocol. Patients experiencing AEs attributed to modakafusp alfa may continue study treatment with the same dose, may have modakafusp alfa treatment held, may have their dose reduced, or may be permanently discontinued from the study. Patients who have study drug held because of treatment-related or possibly related AEs may resume study drug treatment after resolution of the AE at the same dose level or at a reduced dose, depending on the nature and severity of the AE and whether it is the first occurrence or is recurrent.

**Table 8.b** and **Table 8.c** provide general dose modification recommendations for nonhematologic and hematologic toxicities, respectively. **Table 8.d** provides dose modification recommendations for bleeding TEAEs to mitigate the risk of fatal hemorrhagic events. If the modakafusp alfa dose is withheld on the basis of these criteria, clinical and laboratory re-evaluation should be repeated at least weekly or more frequently, depending on the nature of the toxicity observed, until the toxicity resolves to Grade  $\leq 1$  or baseline. If there are transient laboratory abnormalities that, based on investigator assessment, are not clinically significant or drug related, continuation of therapy without dose modification is permissible on discussion with the sponsor.

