## Protocol Amendment 1 v2 Summary and Rationale

This section describes the changes in reference to the protocol incorporating Amendment 1 v2. The primary reason for this amendment was to implement new dose modification guidelines in cases of bleeding treatment-emergent adverse events (TEAEs) as an urgent safety measure to mitigate the risk of fatal hemorrhagic events in response to the observation of a suspected unexpected serious adverse reaction (SUSAR) in the ongoing Study TAK-573-1501.

New dose modification guidelines have been added to this protocol.

In this amendment, minor grammatical, editorial, formatting, and administrative changes not affecting the conduct of the study are included for clarification and administrative purposes only.

Protocol Amendment 1 v2			
Summary of Changes Since the Last Implemented Version of the Approved Protocol			
Change Number	Section(s) Affected by Change	Description of Each Change and Rationale	
	Location	Description	Rationale
1.	8.6.1.3 Criteria for Dose Interruption	Addition of Table 8.d with the dose modifications for modakafusp alfa bleeding TEAEs.	Updated to mitigate the risk of fatal hemorrhagic events.
2.	8.6.1.5 Criteria for Discontinuation	Modification of phase name to indicate “dose escalation” rather than “safety lead-in”. Removal of criteria related to Grade 4 life threatening TEAEs.	Updated to align with changes made in this protocol amendment.
3.	8.8 Permitted Concomitant Medications and Procedures	Added “Platelet transfusion should not be applied only for the purpose of meeting the treatment criterion of platelet count to start a new cycle.”	Updated to align with changes made in this protocol amendment.

Protocol Amendment 1 v2			
Summary of Changes Since the Last Implemented Version of the Approved Protocol			
Change Number	Section(s) Affected by Change	Description of Each Change and Rationale	
4.	8.10.1.2 Low Platelet Count	Addition of mention to reference Table 8.d with the dose modifications for modakafusp alfa bleeding TEAEs	Updated to mitigate the risk of fatal hemorrhagic events.

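### The protocol manages bleeding events as one class, but the SAP prespecifies no grouped, patient-level bleeding count by dose and no link to Grade 4 thrombocytopenia

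*SAP*

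**What the plan says.** **Protocol.** Appendix G (Amendment 1 v2) describes the bleeding rules as introduced "as an urgent safety measure to mitigate the risk of fatal hemorrhagic events", following a SUSAR in Study TAK-573-1501. Section 8.6.1.3 states that Table 8.d "provides dose modification recommendations for bleeding TEAEs to mitigate the risk of fatal hemorrhagic events". That table grades bleeding as a single class and splits Grade 3 by whether Grade 4 thrombocytopenia accompanies it. Section 4.3 names thrombocytopenia and neutropenia as the expected overlapping toxicities, "with the possible clinical manifestation of bleeding and infection". Exclusion criterion 11 (Section 7.2) bars patients at high risk of hemorrhage or on therapeutic anticoagulation. Section 8.3.1 makes thrombocytopenia of Grade 3 or higher with clinically significant bleeding a DLT. Section 10.1.3 designates only IRRs as AESIs.

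**SAP.** Section 6.7.1: "Treatment-emergent AEs will be summarized by MedDRA system organ class (SOC) and preferred term (PT) by dose level". Separate tables cover Grade 3 or higher, serious, Grade 5, discontinuation and dose-modification events, all by dose level and phase. A patient is counted once within each organ class and once within each preferred term. On pooling, "the following hematologic abnormalities coded to MedDRA preferred terms in the Investigations SOC will be pooled with the appropriate clinical terms"; five terms are listed, all cytopenias. Section 6.7.2: "In this study, infusion-related reactions (IRR) are considered as AESIs". The readable safety section contains no bleeding group, bleeding term list or standard query.

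**The concern.** The protocol asks investigators to act on bleeding as one concept, and to act differently according to concurrent Grade 4 thrombocytopenia. The safety tables are not organised that way. A reader comparing dose levels will see separate rows for separate bleeding terms. No row gives the number of patients who bled, the number who bled at Grade 3 or higher, or how many of those had Grade 4 thrombocytopenia.

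This matters because TEAE frequency and severity is a phase 1 primary endpoint (Protocol 5.2.1), and because the choice of phase 2a doses and of the RP2D rests on an integrated reading of safety with other data (Protocol 4.4 and 6.1). With cohorts of about 6 and arms of about 20, spreading a handful of events over several rows can hide a difference or a signal.

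**Working it through.** **1. The plan's own safety figure.** SAP Section 4.0 gives the chance of seeing at least one AE in 20 patients. The formula is 1 − (1 − p)^20:

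| True rate p | Stated | Recomputed |
|---|---|---|
| 5% | 64% | 64.2% |
| 10% | 88% | 87.8% |
| 15% | 96% | 96.1% |
| 20% | 99% | 98.8% |

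The figures reproduce. They describe one AE category, so they apply to bleeding as a whole only if bleeding is counted as one category.

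**2. Can the patient count be recovered from the rows?** Suppose three bleeding terms show 2, 1 and 1 patients in an arm of 20 (assumed counts). The number of distinct patients lies between the largest row (2) and the sum (2 + 1 + 1 = 4). Clopper-Pearson 95% intervals, the SAP's method:

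- 2/20 = 10% (1.2% to 31.7%)
- 4/20 = 20% (5.7% to 43.7%)

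In a phase 1 cohort of 6, rows of 1 and 1 fit either 1/6 = 17% (0.4% to 64.1%) or 2/6 = 33% (4.3% to 77.7%). Organ-class rows do not settle it: each includes non-bleeding terms, and a patient with bleeding in two organ classes is counted in both.

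**3. Effect of splitting on the common-event table.** SAP 6.7.1 sets a 10% threshold per preferred term. Assume a true bleeding rate of 20%, split evenly over four non-overlapping terms of 5% each. In 20 patients the threshold is 2, and P(X ≥ 2) = 1 − (1 − q)^20 − 20q(1 − q)^19:

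- Grouped, q = 0.20: 1 − 0.0115 − 0.0576 = 93%
- One given term, q = 0.05: 1 − 0.3585 − 0.3774 = 26%

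In 40 patients (threshold 4) the figures are 97% and 14%. For n = 20 and three to five terms, a true rate of 10% gives 61% grouped against 6% to 14% per term; a true rate of 30% gives 99% against 34% to 61%. The documents give neither a bleeding rate nor a number of terms, so these figures only illustrate.

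**4. Can bleeding be linked to platelets from the planned data?** Partly. Appendix A schedules hematology on Days 1, 8, 15 and 22 in Cycles 1 and 2 (the Cycle 1 Day 1 test may be omitted if screening results are less than 3 days old), on Days 1 and 15 in Cycles 3 to 6, and on Day 1 only from Cycle 7. If concurrent meant within 7 days either side (an assumed window), a Day 1 count covers 7 + 1 + 7 = 15 of the 28 days, ignoring visit windows, and leaves 28 − 15 = 13 without a scheduled count. Day 1 counts must also meet the Section 8.6.1.2 platelet criterion before a new cycle starts, whereas Section 4.5.1.2 places the lowest mean counts at Day 8 or 15 of the first two cycles (1.5 mg/kg Q4W). A cross-tabulation therefore needs unscheduled counts and AE records as well, and a category for patients with no count near onset.

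**The case against.** The strongest reply is that the SAP follows the protocol. Both name IRRs alone as AESIs, and the protocol kept that designation through two bleeding-related amendments. Every bleeding term will be tabulated by dose, and all deaths listed. Related thrombocytopenia of Grade 3 or higher with significant bleeding is a DLT, listed by patient and dose. Table 8.d cases that lead to stopping modakafusp alfa should appear in the discontinuation table. Platelet profiles are produced for each dose level. The cytopenia pooling merges two names for one finding, which differs from grouping diagnoses by concept. No formal dose comparison is planned.

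All of this stands, and it limits the size of the point. None of it yields a de-duplicated count: the DLT route covers only related events in phase 1, primarily in Cycle 1; the discontinuation table is also split by term; and the platelet displays are not tied to bleeding.

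Four stronger readings are tempting and are not supported:

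- **That a fatal bleed triggered the measure.** Appendix G states the aim and refers to a SUSAR in another study; it gives neither the type nor the outcome of that event.
- **That bleeding by dose is never reported.** Individual terms are; only the grouped patient count is absent.
- **That bleeding is the one harm the sponsor acted on.** IRRs and cytopenias have their own management rules.
- **That the SAP contradicts the protocol.** It does not. The SAP's date is not visible, so it may predate Table 8.d, and some protocol text near these provisions is redacted.

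**Conclusion.** The point holds as a reporting gap. The plan gives bleeding by individual term and dose, but prespecifies no number of patients with any, Grade 3 or higher, serious or Grade 5 bleeding as a group, and no tabulation against Grade 4 thrombocytopenia, although the protocol draws exactly that distinction. In the assumed example, the same rows are compatible with rates of 10% and 20% in an arm of 20. The conclusion assumes that bleeding will be coded to more than one preferred term, which follows from coding by site but is not stated in the documents, and that the redacted sections hold no grouped bleeding analysis. SAP 6.7, where one would be expected, is readable and has none. The gap applies equally to phase 1, so it does not depend on phase 2a being run. It is a cheap improvement, not an error in the SAP.

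**What to change.** In SAP 6.7.1 and 6.7.2, add a grouped bleeding TEAE category, defined by a fixed preferred-term list or the standard MedDRA haemorrhage query and locked before database lock. Tabulate by dose level and phase the number and percentage of patients with:

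- any-grade bleeding;
- Grade 3 or higher bleeding;
- serious bleeding;
- Grade 5 bleeding.

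Count each patient once per row, whatever the number of terms.

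Add a cross-tabulation with concurrent Grade 4 thrombocytopenia, using scheduled and unscheduled platelet counts and AE records. State in advance the interval around onset that counts as concurrent, and show patients with no platelet count in that interval as a separate category instead of treating them as free of thrombocytopenia.

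The cost is agreement on a term list and one or two extra tables from AE and hematology data already collected. The AESI designation, Table 8.d and every other clinical rule are unchanged.
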